9.5.1. Unblinding at Interim Analyses

Interim analyses for safety and efficacy will be conducted, using unblinded data, under the guidance of an independent Data Monitoring Committee (DMC). The DMC will consist of at least 3 members, including at least 1 clinician and 1 statistician. The DMC will communicate any recommendations based on interim analysis to the Lilly Senior Management Designee (SMD). If necessary, the SMD may form an Internal Review Committee (IRC) to review and act upon the recommendations of the DMC. See Section 12.2.15 for details on the conduct of interim analyses.

9.5.2. Emergency Unblinding

In case of an emergency, the investigator has the sole responsibility for determining if unblinding of a patient's treatment assignment is warranted. Patient safety must always be the first consideration in making such a determination. If the investigator decides that unblinding is warranted, the investigator should make every effort to contact the Lilly CRP prior to unblinding a patient's treatment assignment unless this could delay emergency treatment of the patient. If a patient's treatment assignment is unblinded, Lilly must be notified immediately.

Emergency unblinding for AEs must be performed through the IWRS. This option may be used ONLY if the patient's acute well-being requires knowledge of the patient's treatment assignment, or if the patient discontinues treatment due to disease progression based upon RECIST Version 1.1 (see Attachment 5) and knowledge of the patient's treatment assignment is deemed essential to the selection of the patient's next treatment regimen. In the case of disease progression, the investigator must consult with the Lilly CRP prior to unblinding.

All calls resulting in an unblinding event are recorded and reported by the IWRS. If the investigator or patient becomes unblinded, that patient will undergo postdiscontinuation follow-up (Attachment 1).

9.5.3. Inadvertent Unblinding

Every effort will be made to blind both the patient and the investigator to the identity of the treatment, but the inadvertent unblinding of a patient may occur. A double-blind study design is known to be imperfect in the oncolytic setting because the potential for individual unblinding exists due to treatment-related signs and symptoms. If an investigator, site personnel performing assessments, or patient is unblinded, the unblinding will not be sufficient cause (in and of itself) for that patient to be discontinued from study therapy or excluded from any safety or efficacy analyses.

Additionally, there may be ethical reasons to have the patient remain on the study treatment. For patients to continue on study treatment in the event of unblinding, the investigator must obtain specific approval from a Lilly CRP for the patient to continue in the study.

9.6. Concomitant Therapy

Appropriate documentation of all forms of premedications, supportive care, and concomitant medications must be captured at each visit in the eCRFs and should be recorded throughout the patient's participation in the study. Concomitant medications and supportive care therapies must also be documented at the time of discontinuation and at the 30-day short-term follow-up visit.

With the exceptions listed in the sections below, therapies for cancer (including specifically aromatase inhibitors, anti-estrogens other than fulvestrant, chemotherapy, and immunotherapy) will not be permitted while patients are on study treatment. Use of megestrol acetate as an appetite stimulant is not permitted.

Modulators of CYP3A

Abemaciclib is extensively metabolized through oxidation by CYP3A. In clinical drug interaction studies,

- coadministration of clarithromycin, a strong CYP3A inhibitor, increased exposure (AUC) to abemaciclib by 3.4-fold (Study I3Y-MC-JPBE), and
- coadministration of rifampin, a strong CYP3A inducer, decreased exposure to abemaciclib by 95% (Study I3Y-MC-JPBF).

Strong inhibitors of CYP3A (given via non-topical routes of administration) should be substituted or avoided if possible ([Attachment 8](#)). This includes grapefruit or grapefruit juice. In particular, avoid oral administration of the very strong CYP3A inhibitor, ketoconazole.

If coadministration with a strong CYP3A inhibitor is unavoidable, investigators should reduce the dose of abemaciclib by 50 mg at the start of CYP3A inhibitor treatment. That is, for patients receiving 150 mg twice daily, reduce the dose to 100 mg twice daily. For patients who have already dose reduced to 100 mg twice daily for tolerability, reduce the dose further to 50 mg twice daily. Alternatively, the investigator may consider suspending abemaciclib for the duration of the CYP3A inhibitor medication. Dose suspensions ≥ 28 days must be discussed with Lilly CRP/CRS.

Upon discontinuation of the strong CYP3A inhibitor, the dose of abemaciclib may be re-escalated to the dose that was used before starting the strong inhibitor after a sufficient washout period (3-5 half-lives of the strong inhibitor). Re-escalation of the abemaciclib dose requires review and approval from Lilly CRP/CRS.

Inducers of CYP3A should be substituted or avoided if possible ([Attachment 8](#)).

Coadministration with a CYP3A inducer ≥ 28 days must be discussed with Lilly CRP/CRS.

Transporter Substrates

At clinically relevant concentrations, abemaciclib inhibits the transporters P-glycoprotein, breast cancer resistance protein, organic cation transporter 2 (OCT2), multidrug and toxin extrusion protein 1 (MATE1), and MATE2-K. The observed serum creatinine increase in clinical studies with abemaciclib is likely due to inhibition of tubular secretion of creatinine via OCT2, MATE1, and MATE2-K. In vivo interactions of abemaciclib with narrow therapeutic index substrates of these transporters, such as digoxin and dabigatran, may occur.

9.6.1. Surgery and/or Radiotherapy for Locally Advanced Breast Cancer

A patient with locally advanced breast cancer may receive surgery ± radiotherapy if study treatment renders the tumor operable. However, such a patient should not receive study treatment for the period beginning at least 7 days prior to surgery and continuing until at least 14 days after completion of surgery ± radiotherapy to allow for tissue healing and recovery. There is no restriction on the duration of this period without study treatment and, after this period ends, study treatment and protocol procedures ([Attachment 1](#)) should either resume based upon the most recent cycle completed prior to surgery ± radiotherapy or the patient should be discontinued from study treatment. Importantly, a patient who receives surgery ± radiotherapy for locally advanced breast cancer is not considered noncompliant and does not incur a protocol deviation.

9.6.2. Radiotherapy

Except as described in Section 9.6.1, radiotherapy is not permitted without permanent discontinuation from study treatment. Except for a patient with locally advanced breast cancer rendered operable by study treatment who subsequently undergoes surgery + radiotherapy, all other patients requiring radiotherapy should discontinue permanently from study treatment and have a tumor assessment of the lesion(s) before receiving radiotherapy.

9.6.3. Supportive Care

Patients should receive full supportive care to maximize quality of life. Patients will receive supportive care as judged by their treating physician. If it is unclear whether a therapy should be regarded as supportive care, the investigator should consult the Lilly CRP. Use of any supportive care therapy should be reported in the eCRFs.

9.6.4. Growth Factors

Growth factors should not be administered to a patient to satisfy study inclusion criteria.

Growth factors may be administered in accordance with ASCO guidelines (Smith et al. 2015). Dosing of study drug must be suspended if the administration of growth factors is required and must not be recommenced within 48 hours of the last dose of growth factors having been administered. Following the administration of growth factors, the dose of study drug must be reduced by 1 dose level on recommencement, if a dose reduction for the specific event necessitating the use of the growth factors has not already occurred.

9.6.5. Supportive Management for Diarrhea

At randomization, patients should receive instructions on the management of diarrhea. In the event of diarrhea, supportive measures should be initiated as early as possible. These include the following:

- At the first sign of loose stools, the patient should initiate anti-diarrheal therapy (for example, loperamide) and notify the investigator/site for further instructions and appropriate follow-up.
- Patients should also be encouraged to drink fluids (for example, 8 to 10 glasses of clear liquids per day).
- Site personnel should assess response within 24 hours.
- If diarrhea does not resolve with anti-diarrheal therapy within 24 hours to at least Grade 1, blinded study drug should be suspended until diarrhea is resolved to at least Grade 1.
- When blinded study drug recommences, dosing should be adjusted as outlined in Section 9.4.1.1.1.1 and Table JPBL.9.3.

In severe cases of diarrhea, the measuring of neutrophil counts and body temperature and proactive management of diarrhea with antidiarrheal agents should be considered.

If diarrhea is severe (requiring IV rehydration) and/or associated with fever or severe neutropenia, broad-spectrum antibiotics such as fluoroquinolones must be prescribed.

Patients with severe diarrhea or any grade of diarrhea associated with severe nausea or vomiting should be carefully monitored and given intravenous fluid (IV hydration) and electrolyte replacement.

9.6.6. Bisphosphonates and RANK-L Targeted Agents

Patients with bone metastases present on baseline imaging may be appropriately treated with bisphosphonates or RANK-L targeted agents (for example, denosumab), per respective approved labels. Initiation of treatment with bone-modifying agents must begin at least 7 days prior to randomization. Patients receiving bisphosphonates or RANK-L targeted agents should not switch treatments (for example, replace a bisphosphonate with denosumab) while on study treatment. However, exceptional cases without evidence of PD may be considered in consultation with the Lilly CRP. These exceptional cases will not incur a protocol deviation.

9.6.7. Ovarian Suppression with Gonadotropin-Releasing Hormone Agonists

Patients who are postmenopausal due to ovarian suppression should continue GnRH agonist therapy during study treatment.

9.7. Treatment Compliance

Treatment compliance information for study drugs will be collected through counts at each visit, and the number of solid oral dosage units taken relative to the number expected to be taken will

be summarized for each cycle. The patient must take $\geq 75\%$ of the planned doses for assigned study drug in a cycle to be deemed compliant. Similarly, a patient may be considered noncompliant if she is judged by the investigator to have intentionally or repeatedly taken $\geq 125\%$ of the planned doses of study drug in a cycle.

Importantly, a patient who receives surgery \pm radiotherapy for locally advanced breast cancer is not considered noncompliant and does not incur a protocol deviation. For additional information, refer to Section [9.6.1](#).

Potential discontinuation of a patient due to study drug noncompliance will be discussed between the investigator and the Lilly CRP or clinical research scientist before any determination is made to discontinue the patient.

10. Efficacy, Health Outcome/Quality of Life Measures, Safety Evaluations, Sample Collection and Testing, and Appropriateness of Measurements

Written informed consent must be obtained prior to any study-specific pretreatment evaluations.

Study procedures related to efficacy, safety, health outcome/quality of life measures, sample collection, and testing assessments and their timing are described in the sections below and shown in the Study Schedule ([Attachment 1](#)).

10.1. Efficacy Measures

10.1.1. Efficacy Assessments at Baseline and during Study Treatment

Within 28 days of randomization, baseline tumor measurements will be performed on each patient. Computed tomography (CT), including spiral CT, scans and magnetic resonance imaging (MRI) are the preferred methods of measurement. In addition, bone scintigraphy will be performed for all patients at baseline (within 28 days of randomization). However, prior bone scintigraphy (obtained as part of routine clinical care) within 45 days before Day 1 of Cycle 1 is also acceptable. *For only those patients with bone lesions identified by bone scintigraphy at baseline*, all such lesions will be evaluated at baseline by focused studies (X-ray, CT scan with bone windows, or MRI) to enable serial assessment. *For patients with inoperable locally advanced breast cancer*, MRI scan of the breast will be performed at baseline. *For patients with visible tumor (such as skin lesions)*, photography will be performed at baseline and each photographic image of the tumor should include a ruler.

The CT portion of a positron emission tomography (PET)-CT scan may be used as a method of response assessment if the site can document that the CT is of identical diagnostic quality to a diagnostic CT (with intravenous and oral contrast). A PET scan alone or as part of a PET-CT scan may be performed separately as part of routine clinical care but cannot be used to assess response according to RECIST v1.1.

The methods of assessment used at baseline must be used consistently for tumor assessment and will be repeated (with the exception of bone scintigraphy) between Day 1 and Day 7 of every second cycle beginning with Cycle 3 and continuing through Cycle 13 (inclusive), between Day 1 and Day 7 of every third cycle after Cycle 13, and within 14 days of clinical progression. For assessment of response *only in patients with bone lesions identified by scintigraphy at baseline*, the method of assessment used at baseline (X-ray, CT scan with bone windows, or MRI) will be repeated between Day 1 and Day 7 of every second cycle beginning with Cycle 3 and continuing through Cycle 13, between Day 1 and Day 7 of every third cycle after Cycle 13, and within 14 days of clinical progression. Bone scintigraphy should be repeated for all patients between Day 1 and Day 7 of every sixth cycle beginning with Cycle 7, when complete response is identified in target disease, or when progression in bone is suspected. For patients with new lesions identified by post-baseline bone scintigraphy, targeted assessment by X-ray, CT scan with bone windows, or MRI will be performed to confirm findings as described in the

Study Schedule ([Attachment 1](#)). To allow flexibility in tumor assessments, imaging conducted up to 3 days prior to Day 1 of the predefined cycles (as early as Day 26 of the prior cycle) will not be considered a protocol deviation.

For patients continuing treatment after study completion, efficacy assessments (frequency and type of assessments) will be at the discretion of the investigator.

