9.4. Selection and Timing of Doses

Blinded study drug will be taken orally every 12 (\pm 2) hours on Days 1 through 28 of a 28-day cycle, for a total of 56 doses per cycle. Patients should not consume food beginning 1 hour before and ending 1 hour after taking blinded study drug. During all cycles, blinded study drug should be taken at approximately the same times each day. If a patient misses or vomits a dose, that dose should be omitted.

Fulvestrant should be administered at the same time as (or up to 20 minutes after) the morning dose of blinded study drug, except when specified otherwise in the PK Sampling Schedule ([Attachment 7](#)). Fulvestrant will be administered intramuscularly on Days 1 and 15 of Cycle 1, then on Day 1 of Cycle 2 and beyond. For Cycle 3 and beyond, the interval between blinded study drug and fulvestrant may be adjusted based on the judgment of the investigator. In the event of a dose suspension of blinded study drug due to toxicity immediately prior to the beginning of a cycle, the PK Sampling Schedule may require adjustment. In these exceptional circumstances, the Sponsor should be notified.

A cycle is defined as the planned treatment interval of 28 days plus any subsequent delay prior to start of the next cycle. A delay in the start of a cycle due to holidays, weekends, bad weather, or other unforeseen circumstances will be permitted up to 7 days and not counted as a protocol deviation). For each 28-day cycle, a total of 56 doses of blinded study drug will be dispensed. In exceptional cases, for planned delays (including but not limited to vacation or holidays), additional blinded study drug may be dispensed.

A patient may continue to receive study drug(s) until she meets 1 or more of the specified reasons for discontinuation (as described in [Section 7.3.1](#)).

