9.4.1.1.2. Dose Suspension (within a cycle) and Cycle Delays

Both dose suspension (within a cycle) and cycle delay are allowed up to 14 days to allow sufficient time for recovery from toxicity possibly related to a study drug. In the event of a dose suspension of blinded study drug during Cycle 1, fulvestrant may be administered as scheduled on Cycle 1 Day 15. If a toxicity possibly related to blinded study drug occurs prior to initiating the next cycle, fulvestrant may be administered and blinded study drug suspended until recovery from the toxicity. If fulvestrant is administered but blinded study drug is suspended, the date of fulvestrant administration shall constitute Day 1 of the next cycle. Patients not recovering from toxicity within 14 days beyond the last day of the previous cycle should be considered for dose adjustment or discontinuation of the relevant study drug(s). In exceptional circumstances, a delay >14 days is permitted upon agreement between the investigator and the Lilly CRP.

In the event of a cycle delay due to logistical reasons (for example, due to patient availability), the patient should continue on blinded study drug if the patient has adequate drug supply. If a patient's blinded study drug is interrupted as a result of not having sufficient drug supply, the cycle may be delayed up to 7 days (and not considered a protocol violation). In exceptional circumstances, a delay >7 days is permitted upon agreement between the investigator and the Lilly CRP.

The start of a cycle may be delayed, or a current cycle interrupted, to allow a patient with a locally advanced breast cancer rendered operable by study treatment to receive surgery ± radiotherapy. For additional information, refer to Section 9.6.1.

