10.1.2. Efficacy Assessments during the Study Period Postdiscontinuation Follow-Up

Postdiscontinuation follow-up during the study period will be conducted as described in the Study Schedule ([Attachment 1](#)).

For those patients who are randomized and never receive study treatment or those who discontinue study treatment without objectively measured PD, the investigative sites will continue to monitor patients and periodically evaluate tumor response approximately every 8 weeks for the first 12 months following randomization and thereafter approximately every 12 weeks by the same method used at baseline and throughout the study until the patient has objective disease progression, or until the final analysis of PFS. After the patient has objective disease progression, radiologic tests are no longer required and the patient will be followed up approximately every 12 weeks (\pm 14 days) until the patient's death or overall study completion.

Lilly will continue to collect survival data on all patients but may reduce data collection for other efficacy data. Lilly will notify investigators when this reduced data collection can begin.

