- g Blinded study drug should be administered orally Q12H on Days 1 through 28 of each cycle; patients should not consume food beginning 1 hour before and ending 1 hour after taking blinded study drug. Fulvestrant 500 mg should be administered intramuscularly into the buttocks slowly (1 to 2 minutes per injection) as two 250-mg injections, one in each buttock; however, for patients with moderate hepatic impairment (defined as Child-Pugh Class B), including any patient who develops moderate hepatic impairment during study treatment, fulvestrant 250 mg should be administered intramuscularly into the buttock slowly (1 to 2 minutes) as one 250-mg injection.

Study Schedule, Protocol I3Y-MC-JPBL (continued)

- h Formalin-fixed paraffin-embedded tumor tissue (either block or 15-20 unstained slides) should be requested at the time of randomization. However, if this sample is not available for a patient, it will not constitute a protocol deviation.
- i Bone scintigraphy is performed locally at baseline (Day -28 to Day -1) for all patients. If available, prior bone scintigraphy (obtained as part of routine clinical care) within 45 days before Day 1 of Cycle 1 is also acceptable. Bone scintigraphy should be repeated for all patients between Day 1 and Day 7 of every sixth cycle beginning with Cycle 7, when complete response is identified in target disease, or when progression in bone is suspected. To allow flexibility in tumor assessments, imaging conducted up to 3 days prior to Day 1 of the predefined cycles (as early as Day 26 of the prior cycle) will not be considered a protocol deviation. Importantly, RECIST v1.1 emphasizes that bone scintigraphy is not adequate to measure bone lesions; however, bone scintigraphy can be used to confirm the presence or disappearance of bone lesions. For patients who discontinue study treatment without objectively measured progressive disease (PD), continue to evaluate tumor response approximately every 6 months until the patient has objective disease progression or until study completion. After the patient has objective disease progression, bone scintigraphy is no longer required and the patient will continue with post-discontinuation follow-up until the patient's death or overall study completion.

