- j One or more of these studies [X-ray, CT scan with bone windows, or MRI] is performed locally at baseline (Day -28 to Day -1), between Day 1 and Day 7 of every second cycle beginning with Cycle 3 and continuing through Cycle 13, between Day 1 and Day 7 of every third cycle after Cycle 13, and within 14 days of clinical progression only for patients with bone lesions identified by bone scintigraphy at baseline. To allow flexibility in tumor assessments, imaging conducted up to 3 days prior to Day 1 of the predefined cycles (as early as Day 26 of the prior cycle) will not be considered a protocol deviation. For patients with new lesions identified by post-baseline bone scintigraphy, targeted assessment by X-ray, CT scan with bone windows, or MRI will be performed to confirm findings. For patients who discontinue study treatment without objectively measured progressive disease (PD), continue to evaluate tumor response approximately every 8 weeks for the first 12 months following randomization and thereafter approximately every 12 weeks by the same method used at baseline and throughout the study until the patient has objective disease progression or until study completion. After the patient has objective disease progression, radiologic tests are no longer required and the patient will continue with post-discontinuation follow-up until the patient's death or overall study completion.
- k mBPI-sf, EORTC QLQ-C30, EORTC QLQ-BR23 and EQ-5D 5L should be administered at baseline (Day -14 to Day -1), Cycle 2 Day 1, and then on Day 1 of every second cycle beginning with Cycle 3 and continuing through Cycle 13, on Day 1 of every third cycle after Cycle 13, and at Short-Term Follow-Up. Patients should complete these assessments before extensive interaction with site staff.
- l Skeletal-Related Events include pathological fracture, spinal cord compression, radiation to bone, and surgery to bone.
- m See Pharmacokinetic Sampling Schedule ([Attachment 7](#)).
- n FSH and estradiol levels are required only for women age <60 years and amenorrheic for at least 12 months.
- o A serum pregnancy test is required only for patients receiving ovarian suppression with a GnRH agonist.
- p For Cycle 2 and beyond, the start of a cycle may be delayed up to 7 days for logistical reasons and up to 14 days to allow sufficient time for recovery from toxicity possibly related to a study drug. Refer to Section [9.4.1.1.2](#).

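### On-treatment scans follow cycle number, so if cycle starts are delayed more often on abemaciclib, PFS is biased slightly in its favour (about 1-2% on the hazard ratio under assumed delay rates)

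*Protocol*

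**What the plan says.** **On treatment.** Protocol Section 10.1.1 schedules tumor imaging "between Day 1 and Day 7 of every second cycle beginning with Cycle 3 and continuing through Cycle 13 (inclusive", then "between Day 1 and Day 7 of every third cycle after Cycle 13, and within 14 days of clinical progression". Attachment 1 repeats this in footnotes b and j. Footnote i applies the same principle to bone scans: "Bone scintigraphy should be repeated for all patients between Day 1 and Day 7 of every sixth cycle beginning with Cycle 7".

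**Cycle length.** Section 9.4 states: "A cycle is defined as the planned treatment interval of 28 days plus any subsequent delay prior to start of the next cycle". On logistics it adds: "A delay in the start of a cycle due to holidays, weekends, bad weather, or other unforeseen circumstances will be permitted up to 7 days". Attachment 1, footnote p, combines both causes, the second being toxicity: "the start of a cycle may be delayed up to 7 days for logistical reasons and up to 14 days to allow sufficient time". Section 9.4.1.1.2 lets the 14 days be exceeded by agreement in exceptional cases.

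**Off treatment.** Section 10.1.2 uses a calendar for patients who stop without progression: "approximately every 8 weeks for the first 12 months following randomization and thereafter approximately every 12 weeks".

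**Dating.** Rule 5 of Table JPBL.12.1 (Section 12.2.7) puts the PFS event on the date progression is documented.

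**Limits on slippage.** Section 9.4.1.1.2 provides: "If fulvestrant is administered but blinded study drug is suspended, the date of fulvestrant administration shall constitute Day 1 of the next cycle". Giving fulvestrant in that situation is allowed, not required. Section 10.1.1 also calls for imaging within 14 days of clinical progression.

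**The concern.** A progression found by a scheduled scan is recorded at the first scan after it occurs. When scans are counted in cycles and cycles can stretch, the scan calendar depends on tolerability. If one arm's cycle starts slip more, its scans come later and so do its recorded progressions. The shift favours the arm with more delay, here presumably abemaciclib, in both the primary log-rank test and the hazard ratio.

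Section 5.1.1 makes unequal delay plausible but does not show it. It reports many dose alterations, mainly from diarrhea in the first cycle. That review was blinded and presumed every alteration to be on abemaciclib. It mainly concerned the 200 mg start. Dose suspension or reduction does not by itself move Day 1.

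**Working it through.** **Inputs from the protocol.** 378 PFS events, 2:1 allocation, hazard ratio (HR) 0.703, one-sided alpha 0.025, control median 6.5 months, exponential PFS (Section 12.1); first dose within 7 days of randomization (Section 9.3); scan schedule and delay rules as above.

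**The plan's own figure.** Schoenfeld's approximation gives power = Φ(√(378 × 2/3 × 1/3) × |ln 0.703| − 1.960) = Φ(9.165 × 0.3524 − 1.960) = Φ(1.270) = 0.898. The stated 90% is reproduced. The abemaciclib median is 6.5/0.703 = 9.25 months, a gain of 2.75 months, also as stated.

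**From HR bias to type I error.** If a true HR of 1 is estimated as r, one-sided rejection is about Φ(−9.165 × ln r − 1.960). For r = 0.990 this is Φ(0.092 − 1.960) = 0.031. For r = 0.976 it is Φ(0.223 − 1.960) = 0.041.

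**Simulation of r.** Every delay rate below is an assumption. Main setting:
- 420 versus 210 patients, 16-month uniform accrual, 8% of events being deaths observed exactly.
- Half of toxicity delays absorbed by on-time fulvestrant.
- 30% of progressions found within 14 days through clinical progression.
- Logistical delays of 1-7 days in 20% of cycles in both arms.
- 2% per month stopping without progression, then scanned by calendar from randomization.

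The analysis is an unstratified log-rank test at the 378th event. Rejection rates have a Monte Carlo SE of about 0.0012 in the main setting and 0.0017 in the other.

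| Toxicity delay of cycle start, abemaciclib vs placebo | Main setting: rejection (median HR) | No logistical delays or stopping: rejection (median HR) |
|---|---|---|
| A: 7 days, 10% vs 3% of cycles | 0.031 (0.993) | 0.036 (0.986) |
| B: 7 days, 20% vs 5% | 0.032 (0.990) | 0.041 (0.976) |
| C: 14 days, 15% vs 5% | 0.030 (0.993) | 0.037 (0.986) |
| D: 14 days, Cycles 1-2 only, 30% vs 5% | 0.033 (0.991) | 0.038 (0.983) |

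Main-setting references: 0.026 (HR 1.001) with no toxicity delays, and 0.026 with equal delays of 10% in each arm.

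**Absorption by fulvestrant.** Case B, main setting, with 0, 25, 50 and 75% of delays absorbed: rejection 0.038, 0.034, 0.032, 0.032; HR 0.985, 0.986, 0.990, 0.994.

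**Under the design alternative.** At a true HR of 0.703 the median estimate is 0.705 without toxicity delays, 0.699 in case B (0.699/0.705 = 0.991), and 0.705 in case B with calendar-anchored scans.

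**Hand check of the lag.** In case B a two-cycle scan interval lengthens by 2 × 7 × (0.20 − 0.05) × 0.5 = 1.05 days. The mean wait for a scan rises by about half of that, and this applies to about 70% of progressions: roughly 0.4 days, inside the simulated 0.2-0.6 days. This is small against a 6.5-month median. The HR moves more than the lag suggests because events cluster at scan visits, and a slight shift places one arm's events behind the other's in rank. Logistical delays in both arms spread the clusters and weaken the effect.

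**Different model set-ups.** A model with a 0-7 day start lag, logistical delays in 15% of cycles, and toxicity delays of 3-14 days in 3% of control and 6-25% of abemaciclib cycles gave observed HR over equal-delay HR, at a true HR of 0.703, of:
- 0.993 to 0.962 with no events found off schedule;
- 0.986 to 0.972 with 20% off schedule;
- 0.998 to 0.985 with 40% off schedule.

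A cruder model with scheduled scans only gave 0.980 to 0.947. Further runs of the assumed cases gave null HRs between 0.980 and 0.997. Every unequal-delay scenario favoured abemaciclib.

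**Corrections.** Under the null in the main setting, calendar-anchored scans in case B give 0.028 (HR 0.999). Interval-censored PFS on actual scan dates gives 0.026-0.027 (HR 0.999-1.001) in cases A-D. That check used an exponential model, which matches the simulated truth; a real analysis needs a flexible baseline hazard.

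**The case against.** The strongest reply is that the necessary condition, more cycle-start delay on abemaciclib, appears nowhere in the documents. Table JPBL.9.2 manages toxicity by suspending, reducing or stopping blinded drug, none of which moves Day 1. Amendment (b) (Section 5.2) deliberately clarified fulvestrant dosing during suspensions, and on-time fulvestrant keeps the cycle clock running. In the main setting the shift is nearer 1% than 2%. Cases A-C hold the excess delay constant over all cycles although the reported problem was mostly first-cycle diarrhea, and the 50% absorption share is arbitrary. More toxicity-related stopping on abemaciclib would move more of that arm to calendar scans and reduce the bias; this was not varied. Sections 12.2.6 and 12.2.13 already summarize dose delays. The main SAP (v4) and the Central Review SAP, which may hold a relevant sensitivity analysis, were not among the documents reviewed.

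Most of this stands and keeps the point minor. It does not remove the mechanism. Fulvestrant during suspension is optional, the protocol allows the cycle start itself to slip for toxicity, and case D, confined to the first two cycles, gives about the same result as the others. A summary of dose delays does not show when scans were done. No claim is made that the main SAP lacks the analysis.

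**Conclusion.** The concern holds as a conditional, minor design weakness. The mechanism and its direction follow from the protocol text; the size does not. Under the assumed delay rates the HR is pulled about 1-2% toward abemaciclib: about 1% in the main setting and up to 2.4% without logistical delays and stopping. Other plausible inputs run from near 0 to about 5%. One-sided type I error rises from 0.026 to 0.030-0.033 in the main setting. The bias is nil if delays are equal between arms or if on-time fulvestrant absorbs every one. It could matter only for a borderline PFS result.

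**What to change.** **1. For data already collected.** Tabulate actual scan times and cycle-start delays by arm, beside the summary planned in Section 12.2.6. Add a PFS sensitivity analysis that treats progression as interval-censored between actual scan dates, with a flexible baseline hazard, unless SAP v4 already contains one. Do not rely on re-dating to nominal visits alone: for a delayed patient that places progression before any scan showed it. Leave Table JPBL.12.1 unchanged.

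**2. As a design correction in Section 10.1.1 and Attachment 1, footnotes b, i and j.** Anchor on-treatment imaging to weeks from Cycle 1 Day 1, so that cycle delays and dose suspensions do not move it. The nominal intervals stay the same:
- Cycle 3 Day 1 is 2 × 28 = 56 days (week 8), and Cycle 13 Day 1 is 12 × 28 = 336 days (week 48), so scans are every 8 weeks to week 48.
- Every third cycle is 84 days, so scans are then every 12 weeks.
- Every sixth cycle is 168 days, so scintigraphy is every 24 weeks.

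Keep the present window and the scan within 14 days of clinical progression.

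Cycle 1 Day 1 is a better anchor than randomization. First dose may fall on day 7, so an undelayed Cycle 3 Day 1 can be day 7 + 56 = 63, whereas a week-8 window counted from randomization (−3 to +6 days) closes on day 62. The remaining offset from the off-treatment calendar is at most 7 days and is fixed before treatment starts. The new wording should not override surgical breaks, and should state how imaging resumes after them consistently with Sections 9.6.1 and 10.1.3.

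**Cost.** One table, one sensitivity analysis and revised schedule wording. A delayed patient may need an imaging visit separate from Day 1. No extra patients and no change to dosing or primary censoring rules. SAP addendum Section 4.3 lists the final PFS analysis before the 05 May 2017 cut-off, so item 2 cannot change the PFS data already collected; item 1 can still be done.
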